### 6. RANDOMIZATION

For the double-blind, vehicle-controlled phase of the study, subjects will be randomized at a ratio of 2:1 to receive tapinar of cream, 1% or vehicle cream as follows:

Randomization in Double-Blind, Vehicle-Controlled Phase			
Regimen	Number of Subjects		
Tapinarof cream, 1% once daily for 12 weeks	Approximately 333 Subjects		
Vehicle cream once daily for 12 weeks	Approximately 167 Subjects		

Randomization will be stratified by baseline PGA score so that subjects with mild and severe psoriasis (PGA scores of 2 and 4, respectively) will be limited to approximately 10% each of the total randomized population, and approximately 80% will have a PGA score of 3, signifying moderate disease.

The randomization lists will be generated using a validated system, which involves a pseudo-random number generator so that the resulting sequence of treatments will be both reproducible and non-predictable. Access to the codes will be controlled and documented.

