### 11. DATA CONVENTIONS FOR ANALYSIS

### 11.1 General Statistical Principles

All statistical tests will be performed at the 0.05 (two-sided) level of significance.

All observed and derived variables (e.g., change from baseline, percentage change from baseline, and response status) that are analyzed or summarized will be listed by subject. Descriptive statistics will provide an overview of the efficacy and safety results. For categorical parameters, the number and percentage of subjects in each category will be presented. The denominator for percentage will be appropriate for the purpose of the analysis. For continuous parameters, descriptive statistics will include number of subjects, mean, standard deviation (SD), median, minimum, and maximum.

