### 12.7.3 Exploratory Efficacy Endpoints

The exploratory endpoints to further characterize the efficacy of tapinar of cream, 1% compared with vehicle control over time are:

- Time (days) to achieving a PGA treatment response, defined as days from date of first dose until achieving a PGA score of 0 or 1 with a minimum 2-grade improvement from Baseline. Subjects who have no PGA response will be censored at the date of their last PGA assessment.
- Proportion of subjects with a PGA score of 0 or 1 at Weeks 2, 4, and 8
- Proportion of subjects who achieve a PGA treatment response at Weeks 2, 4, and 8
- Mean absolute and percent change in PASI score from Baseline to Weeks 2, 4, 8, and 12
- Proportion of subjects with ≥ 50% improvement in PASI score (PASI-50) from Baseline to Weeks 2, 4, 8, and 12
- Proportion of subjects with ≥ 75% improvement in PASI score (PASI-75) from Baseline to weeks 2, 4, and 8
- Proportion of subjects with ≥ 90% improvement in PASI score (PASI-90) from Baseline to weeks 2, 4, and 8
- Mean change in %BSA affected from Baseline to Weeks 2, 4, and 8
- Mean % change in %BSA affected from Baseline to Weeks 2, 4, 8, and 12.

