### 12.8.2 Secondary and Exploratory Efficacy Analyses

The same methods as discussed for the primary analyses will be used to analyze all dichotomized and continuous secondary endpoints. The secondary efficacy endpoints will be tested sequentially in the order listed. Testing will stop if non-significance (2-sided  $p \ge 0.05$ ) is observed as described in Section 11.6.

Other exploratory efficacy endpoints will be analyzed using CMH test for proportions, and analysis of covariance (ANCOVA) model for continuous variables. CMH tests will be stratified by baseline PGA score, and ANCOVA models will include baseline PGA score as a covariate (2, 3 or 4), and baseline value of the endpoint as a continuous covariate. For proportions, the same MI approach describe above will be taken to deal with missing data. For continuous variables, the standard MI procedures for ANCOVA will be followed. Least squared means of treatment difference (tapinarof – placebo) along with the 95% CI will be reported.

Time to achieving a PGA success will be analyzed with the Kaplan Meier method in the ITT population based on Observed Cases. Treatment groups will be compared using a log-rank test. Estimates of median time to response from Kaplan Meier distribution will be computed. A Kaplan-Meier figure will also be generated.

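### Time to PGA response: the log-rank test names no strata, and with no Week 12 limit off-treatment Week 16 responses can enter the Kaplan-Meier curve and median

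*SAP*

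**What the plan says.** The analysis is in SAP 12.8.2: "Time to achieving a PGA success will be analyzed with the Kaplan Meier method in the ITT population based on Observed Cases". Then "Treatment groups will be compared using a log-rank test", and "Estimates of median time to response from Kaplan Meier distribution will be computed". No stratification factor or covariate is attached to the test. In the same section, "CMH tests will be stratified by baseline PGA score", and the ANCOVA models include baseline PGA. SAP 12.8.1 stratifies the primary test in the same way. Baseline PGA is also the randomisation factor (SAP 6: "Randomization will be stratified by baseline PGA score"), with about 10%, 80% and 10% of subjects at PGA 2, 3 and 4.

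SAP 12.7.3 counts time from first dose to first response and adds: "Subjects who have no PGA response will be censored at the date of their last PGA assessment". It gives no last visit for either events or censoring. PGA is scheduled at the Week 16 Follow-up visit (Protocol Table 1 and Section 7.4). That visit falls about four weeks after treatment ends and is for subjects who do not enter the open-label study. Footnote a of Table 1 adds premature withdrawals.

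The Protocol lists the endpoint in Section 10.4.2.2 but gives no time-to-event method that would settle either question.

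**The concern.** There are two separate gaps.

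**Strata.** The response hurdle differs by baseline score. A score of 0 or 1 with at least a 2-grade improvement means that PGA 2 must reach 0, PGA 3 must fall at least two grades and PGA 4 at least three. Baseline PGA may therefore be prognostic for this endpoint. Leaving it out departs from the other PGA responder tests and can cost some power.

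**Off-treatment tail.** A responder has the event at first response and leaves the risk set. A non-responder who rolls over is censored at about Week 12. The only subjects still at risk at Week 16 are non-responders who did not roll over and early withdrawals who attended follow-up. A first response there counts as an event, although it occurs off drug in a small, selected group. In a Kaplan-Meier curve a small risk set makes each event a large step, and the planned median is read from that curve.

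**Working it through.** **Inputs from the documents.** 333 vs 167 subjects; response 40% vs 15%, or 35% vs 20%; up to 25% lost by Week 12 (SAP 7). Two-sided 0.05 (SAP 11.1). Strata of about 10/80/10%, that is 50/400/50 of 500 (SAP 6).

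**Assumptions not in the documents.** Share not rolling over, 5–50% (10% and 30% used below). Probability of a first response at Week 16, 5–10%. Stratum-specific response rates and pace of response. Cumulative response by Week 12 equal to the Week 12 rate.

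**1. The plan's own figure.** SAP 7 states primary-endpoint power above 99% and above 94%. At 40% vs 15% all methods give more than 99.9%. At 35% vs 20% the results are 93.8% (Fisher exact), 94.5% (pooled chi-square) and 93.2% (continuity-corrected), which agree with the stated figure to about one point. The plan states no power for time to response.

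**2. Implied hazard ratios** (proportional hazards):
- 40% vs 15%: ln(0.60)/ln(0.85) = 3.14
- 35% vs 20%: ln(0.65)/ln(0.80) = 1.93

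**3. Median.** At 40% vs 15% the curves stand at 0.60 and 0.85 at Week 12, so neither median is reached on treatment. The tapinarof median is reached at Week 16 if 0.60 × (1 − q) ≤ 0.50, which gives q ≥ 1/6 = 16.7% of those at risk.

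**4. Risk set at Week 16, 10% not rolling over.** The lower figure assumes 25% loss and no return of those subjects at follow-up.
- Tapinarof: 333 × 0.60 × 0.10 ≈ 20, or × 0.75 ≈ 15. One event moves the curve 0.60/20 = 3.0 to 0.60/15 = 4.0 points. Three events of 15, or four of 20, bring it to 0.48, so the median falls at about Day 113.
- Vehicle: 167 × 0.85 × 0.10 ≈ 14, or × 0.75 ≈ 11. One event moves the curve 6.1 to 7.7 points.

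With 30% not rolling over, the risk sets are about 45–60 and 32–43. One event moves the curves 1.0–1.3 and 2.0–2.7 points, and the tapinarof median needs 8 to 10 events.

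**5. Power of the test at 35% vs 20%.** Simulation with visits at Days 15, 29, 57, 85 and 113, 25% dropout and 1,500 runs per row (Monte Carlo standard error about 0.8 points). Entries are power in %.

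| Strata | Not rolling over | Week 16 first response, tapinarof/vehicle | Unstratified, to Week 12 | Stratified, to Week 12 | Unstratified, to last PGA | Stratified, to last PGA |
|---|---|---|---|---|---|---|
| alike | 10% | 5%/5% | 89.1 | 88.9 | 88.7 | 88.9 |
| alike | 30% | 5%/5% | 90.4 | 90.5 | 89.4 | 89.3 |
| alike | 30% | 5%/10% | 89.1 | 89.1 | 83.5 | 83.4 |
| strongly different | 10% | 5%/5% | 90.0 | 90.2 | 89.8 | 89.7 |
| strongly different | 30% | 5%/5% | 90.6 | 90.2 | 89.6 | 89.7 |
| strongly different | 30% | 5%/10% | 90.0 | 90.2 | 85.3 | 85.7 |
| extremely different | 10% | 5%/5% | 89.6 | 91.2 | 89.7 | 90.6 |
| extremely different | 30% | 5%/5% | 89.8 | 90.6 | 88.7 | 89.5 |
| extremely different | 30% | 5%/10% | 91.6 | 92.5 | 85.8 | 87.3 |

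- Stratifying alone, cut at Week 12: from −0.4 (90.6 to 90.2) to +1.6 points (89.6 to 91.2), so nothing beyond noise unless strata differ extremely.
- Tail alone, unstratified: about 0 to 1 point lost with equal off-drug response; 4.7 to 5.8 points lost with 30% not rolling over and vehicle at 10% vs tapinarof at 5%.
- Both changes together in that unfavourable case: 4.9 (90.2 − 85.3) to 6.7 (92.5 − 85.8) points gained.

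At 40% vs 15% every version exceeds 99%. With equal rates through Week 12, rejection is about 4–6% for every version, within simulation error of 5%.

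**The case against.** The strongest reply is on scope. SAP 1 confines the plan to the double-blind phase. Protocol Table 1 and Section 7.4 place follow-up outside that phase. Every PGA, PASI and %BSA endpoint with a named visit stops at Week 12. On that reading Week 16 was never meant to count. It is a possible reading, but the text does not secure it: SAP 9 keeps Week 16 data as observed cases, SAP 11.4 defines a Week 16 window, and the table in SAP 12.8 analyses the patient-reported outcomes there. Two programmers could properly produce different curves and p-values.

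It is also fair to say that the lack of strata is inferred from silence, that 80% of subjects sit in one stratum, and that the endpoint is exploratory, outside the fixed sequence of SAP 11.6 and without a power claim. All of this stands and limits the weight of the point.

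A reader might infer more than the documents support:
- **That the test is invalid.** An unstratified log-rank test remains valid under stratified randomisation, and the simulated rejection rates show no distortion.
- **That everyone is followed to Week 16.** The last-PGA rule applies only to non-responders, and those who roll over stop at about Week 12.
- **That Week 16 events dominate the p-value.** The large steps belong to the Kaplan-Meier curve. The log-rank test gives each event unit weight.
- **That power is materially at risk.** The loss of about 5 points or more needs 30% not rolling over and twice the off-drug response on vehicle. Neither figure is in the documents.

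**Conclusion.** The point holds as a minor gap in specification. Stratifying is worth about 0 to 2 power points when strata differ. The upper end comes from a separate simulation at a hazard ratio of 1.6 (66.2% to 68.2%), weaker than either design scenario implies. At 40% vs 15% the choice has no practical effect.

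The missing Week 12 limit matters more, and mainly for description: a tapinarof median could be reported that rests on a handful of off-drug responses. That conclusion assumes cumulative first response by Week 12 equals the design rate. Cumulative response also includes subjects who responded earlier and lost the response, so it can be higher; at 50% or more the median would be reached on treatment. The step sizes depend on the assumed rollover share. The textual gaps depend on none of these assumptions. The primary endpoint and the secondary hierarchy are untouched.

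**What to change.** In SAP 12.8.2, specify a log-rank test stratified by baseline PGA (2, 3, 4). In SAP 12.7.3, count responses only through the Week 12 PGA and censor non-responders at their last PGA up to Week 12. Report Week 16 PGA separately as observed cases. If the Week 12 median is not reached, report it as such.

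This is a change of a few phrases. The downside is negligible: a few off-drug first responses leave the time-to-event analysis, though they remain visible in the Week 16 summary, and two strata are small, at about 50 subjects each.

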### 7. SAMPLE SIZE DETERMINATION

It is assumed that the proportion of subjects who achieve PGA score of clear (0) or almost clear (1) with a minimum 2-grade improvement from Baseline at Week 12 will be 40% for subjects receiving tapinarof compared with 15% for subjects receiving vehicle control. With 500 subjects randomized in a 2:1 ratio (approximately 333 subjects receiving tapinarof cream, 1% and approximately 167 subjects receiving vehicle cream) there will be > 99% power for statistical significance (2-sided p< 0.05). If tapinarof response rate is 35%, and vehicle response rate is 20%, the power will be > 94%. Power comes from a Fisher Exact sample size calculation which is conservative. It is assumed that up to 25% of the subjects will be lost to follow-up by 12 weeks. These subjects will be included in the primary analysis in the ITT population using the multiple imputation method as detailed below.

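### The Kaplan-Meier median is the only numerical summary of time to PGA response; it will almost never exist on vehicle and can be a visit-date artefact on tapinarof

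*SAP*

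**What the plan says.** SAP 12.7.3 lists time to PGA treatment response among the exploratory endpoints. Time runs in days from the first dose to the first PGA of 0 or 1 with at least a 2-grade improvement. For the rest: "Subjects who have no PGA response will be censored at the date of their last PGA assessment". No end of follow-up is stated for this endpoint.

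SAP 12.8.2 analyses it in the ITT population on observed cases, with Kaplan-Meier curves, a log-rank test and a figure. On numerical results it says only: "Estimates of median time to response from Kaplan Meier distribution will be computed". It names no hazard ratio, no difference between arms and no confidence interval. For the other endpoints the SAP does commit to an estimate: a relative risk with 95% CI for proportions (12.8.1, carried into 12.8.2) and a least-squares mean difference with 95% CI for continuous variables.

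SAP 7 assumes a Week 12 PGA response of "40% for subjects receiving tapinarof compared with 15% for subjects receiving vehicle control", with 35% against 20% as the alternative. The arms are "approximately 333 subjects receiving tapinarof cream, 1% and approximately 167 subjects receiving vehicle cream". The protocol's Schedule of Assessments places Week 12 at Day 85 ± 2 days.

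**The concern.** A Kaplan-Meier median exists only when the estimated cumulative response reaches 50%. All four planning rates are below that, and the vehicle rates are far below. If the median is missing in one arm, the endpoint yields a p-value and a picture but no number that compares the arms.

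The opposite risk is less visible. The definition works on actual dates, so the last few days of follow-up can push the tapinarof curve through 50% while few subjects remain at risk. The report would then state a median of about 12 weeks for a treatment to which most subjects never responded. A secondary objective is to characterise efficacy over time against vehicle, so this number would be read and quoted.

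**Working it through.** **Inputs from the documents.** Response rates, arm sizes and up to 25% loss: SAP 7. Event and censoring rules: SAP 12.7.3. Visits at Weeks 2, 4, 8 and 12, with Day 85 ± 2 for the last: protocol Schedule of Assessments.

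**Assumed, because the documents give no figures.** Correlation of response between visits, how first responses spread over visits, where visits fall inside the window, and the share of subjects with a Week 16 PGA.

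**Step 1. The plan's own figure.** Full enumeration of the two-sided Fisher test at 333 and 167 gives power above 99.9% for 40% against 15%, and 93.8% for 35% against 20% (pooled chi-square: 94.5%). The SAP states above 99% and above 94%. The second exact value is a shade low, but the inputs are evidently read as intended.

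**Step 2. Nominal days, response kept once gained.** Ever-response then equals the Week 12 rate. With complete follow-up, the median needs at least 167 of 333 or 84 of 167 responders. The binomial probability is 0.0001 on tapinarof at 40%, about 1e-8 at 35%, and below 1e-17 on vehicle at either rate.

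**Step 3. Nominal days, some responders relapse.** The planning rates are the proportions in response at Week 12, so they are a floor for ever-response. To reach 50%, tapinarof needs 50 − 40 = 10 or 50 − 35 = 15 further points; vehicle needs 50 − 15 = 35 or 50 − 20 = 30. The simulated chance of a tapinarof median is about 5% at 45% ever-response, 52% at 50% and 95% at 55%.

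A latent autoregressive model was also run, with 4-week correlation 0.7-0.9 and Week 2, 4 and 8 response at 15, 40 and 80% of the Week 12 rate. It gives ever-response of 44-51% (tapinarof, 40%), 39-46% (tapinarof, 35%), 18-25% (vehicle, 15%) and 24-32% (vehicle, 20%).

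**Step 4. Actual dates.** A hand calculation shows the mechanism. Take tapinarof at 40% ever-response, no loss, first responses split 10/20/40/30% over the four visits, and Week 12 visits spread evenly over Days 83-87.

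- Responded by Week 8: 0.40 × 0.70 = 28%. Still at risk: 72%.
- First response at Week 12: 0.40 × 0.30 = 12%, or 2.4% on each of five days.
- Each day 72/5 = 14.4% leave (2.4% respond, 12% are censored), so the risk sets are 72, 57.6, 43.2, 28.8 and 14.4%.
- Daily factors 1 − 2.4/(risk set): 0.9667, 0.9583, 0.9444, 0.9167, 0.8333. Their product is 0.668.
- Remaining: 0.72 × 0.668 = 0.481, so the curve ends at 51.9%.

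A true 40% is displayed as 51.9%, and a median is declared. The same arithmetic gives 45.9% for a true 35%, 20.4% for 15% and 26.9% for 20%.

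Share of simulated trials in which a median was reached (autoregressive model, with and without 25% loss):

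| Arm and Week 12 rate | Nominal days | Uniform ±2-day scatter |
|---|---|---|
| Tapinarof 40% | 0 to about 60% | about 90-100% |
| Tapinarof 35% | 0-10% | 42-99% |
| Vehicle 15% or 20% | 0% | 0-6% |

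With scatter, only about 35-85 of 333 tapinarof subjects were still at risk when the curve crossed 50%. The low ends carry simulation error: with 200 trials the standard error at 42% is √(0.42 × 0.58/200) = 3.5 points. If response is always kept, the scatter figures are 42-94% at 40%, 8-60% at 35%, and 0% on vehicle. If 5% of Week 12 visits are also 3 to 14 days late, a vehicle median appears in 6-33% of trials, typically with about 2 subjects at risk.

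**Step 5. What a direct estimate would give.** Read the Week 12 rates as cumulative response, without loss. For 40% against 15% the difference is 25 points, with standard error √(0.40 × 0.60/333 + 0.15 × 0.85/167) = 0.0385 and 95% CI about 17 to 33. For 35% against 20% it is 15 points, standard error 0.0405, 95% CI about 7 to 23.

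**The case against.** The endpoint is exploratory and outside the fixed sequence of SAP 11.6. The log-rank test needs no median: reading the planning rates as cumulative response under proportional hazards, its power is above 99.9%, or about 97% in the alternative case (about 91% with a quarter fewer events). The figure also remains valid as a display. This stands, and it limits the point to a reporting improvement.

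PGA response at Weeks 2, 4 and 8 is analysed with a relative risk and 95% CI, and Week 12 is the primary endpoint, so efficacy over time is quantified elsewhere. This stands in part: those are proportions in response at a visit, not time to first response.

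SAP 11.4 says endpoints are analysed by nominal visit, which could be read as removing the date scatter. But 12.7.3 defines this endpoint in days from first dose and censors on a date, and the specific rule is the natural one to program. If 11.4 governs, the artefact goes, but the tapinarof median is again often missing. Either way the SAP should say which applies.

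Week 16 PGAs, taken only in subjects who do not enter the long-term study, would keep some subjects at risk longer and damp the artefact. They do not remove it. With an assumed 15% having such a visit and ever-response of 45%, a median was still declared in 68-97% of trials, against about 5% on nominal days.

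A reader might infer that the vehicle median can never be reached and that the tapinarof median will usually be missing. The documents do not support either. The planning rates are Week 12 prevalences, not cumulative response; the permitted window alone can produce a tapinarof median; and late visits can produce a spurious one on vehicle.

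**Conclusion.** The point holds as a low-cost improvement. At the planning rates the only planned number is almost always absent on vehicle (0-6% of simulated trials within the window). On tapinarof it is either absent or decided largely by the scatter of Week 12 dates (0-60% reached on nominal days, 42-100% with uniform scatter, less in the 35% case if responders never relapse). These ranges rest on assumed correlation, response spread and scatter; the hand calculation rests on the last two and on response being kept.

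It would be wrong to conclude that the effect estimate is missing because the median is not reached. It is missing because SAP 12.8.2 specifies none; two reached medians would still come without a contrast or an interval. Nothing here touches the primary or secondary conclusions.

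**What to change.** In SAP 12.8.2, with a matching line in 12.7.3:

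- Analyse time on nominal visits (Weeks 2, 4, 8, 12), using the 11.4 windows for early termination and unscheduled assessments, and end follow-up for this endpoint at the Week 12 visit.
- Report the Kaplan-Meier cumulative first-response proportion per arm at each visit with 95% CI, and the between-arm difference at Week 12 with 95% CI.
- Keep the log-rank test and the figure. Show the median as secondary, marked as not reached where that applies.

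Reading the curve at exactly Day 85, or using restricted mean time to Day 85, would be a poorer repair on actual dates. Under uniform scatter, 2 of 5 Week 12 visits fall on Days 86-87 and would count as not yet responded, which lowered the Day 85 estimate by about 1-4 points in simulation. The restricted mean gives almost no weight to first responses at Week 12, which were about 22-34% of all first responses.

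The cost is a short SAP edit and a few extra table rows, with no new data. Fixing it before unblinding avoids choosing the summary after seeing the curves.

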### 12.8.3 Other Efficacy Analyses

Change from baseline in DLQI, PSD, SF-36, and Peak Pruritus-NRS will be analyzed using an ANCOVA model with treatment as a main effect, baseline PGA score as a categorical covariate, and baseline value of the endpoint as a covariate. Percent change from baseline in DLQI, PSD and Peak Pruritus-NRS will be summarized and analyzed using the same method.

In addition, the proportion of subjects with at least a 4-point reduction from baseline in the Peak Pruritus-NRS among subjects with a baseline NRS score  $\geq$  4 will be summarized and analyzed following the same method as the dichotomized secondary endpoints. A plot will be used to illustrate this information.

Subject itch diary and in-clinic itch score assessments will be listed and summarized using descriptive statistics by day. If a subject completed diary itch score on the date of in-clinic visit, the itch score assessed in-clinic will be used in the summary. Change from baseline, treatment difference (Tapinarof cream 1% – Vehicle Cream) in mean change from baseline values and its associated 95% CI will be summarized by day. In addition, the treatment difference and its associated 95% CI will be plotted by day.

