## 6.2.2.4. Peak Pruritus-Numeric Rating Scale

The Peak Pruritus-NRS is used to quickly assess itch/pruritus severity over a 24-hour period. The subject will utilize the scale to assess peak pruritus once daily and record the results in their daily diaries. On clinic visit days, the Peak-Pruritis NRS will be assessed in the clinic and not recorded in the diary. An example of the Peak Pruritus-NRS is provided in Appendix 7.

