#### 10.4.4. Analysis of Functional Outcomes and Quality of Life Endpoints

The subject-reported endpoints to examine the effect of study drug on psoriasis symptom severity and the associated impact on daily activities and attitudes are as follows:

- Change in Peak Pruritus-NRS from Baseline at Weeks 2, 4, 8, and 12
- Change over time in psoriasis impact on daily activities, as measured by the DLQI total and individual dimension scores
- Change over time in psoriasis symptoms, as measured by the PSD
- Change over time in physical component score and mental component score, as measured by the SF-36 questionnaire

Change from baseline in DLQI, PSD, SF-36, and Peak Pruritus-NRS scores will be analyzed using an ANCOVA model with treatment as a main effect, and baseline as a covariate.

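### SAP 12.8.3 names no baseline adjustment for the daily itch difference, although the by-visit analysis of the same scale has one; using that model would narrow the daily intervals, probably modestly

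*SAP*

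**What the plan says.** For the patient-reported scales, Peak Pruritus-NRS among them, SAP 12.8.3 analyses change from baseline with an "ANCOVA model with treatment as a main effect, baseline PGA score as a categorical covariate, and baseline value of the endpoint as a covariate". The table in SAP 12.8 applies this to Peak Pruritus-NRS at Weeks 2, 4, 6, 8, 10, 12 and 16. Protocol 10.4.4 has a simpler form of the same model for change in these scores, "using an ANCOVA model with treatment as a main effect, and baseline as a covariate".

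The last paragraph of SAP 12.8.3 turns to the daily itch scores from diary and clinic, which "will be listed and summarized using descriptive statistics by day". It then goes beyond description within each arm: the difference between tapinarof and vehicle "in mean change from baseline values and its associated 95% CI will be summarized by day", and "the treatment difference and its associated 95% CI will be plotted by day". It names no model, covariate or least-squares mean, and does not say how the interval is computed.

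It is the same scale in both places. Under Protocol 6.2.2.4, "The subject will utilize the scale to assess peak pruritus once daily", and SAP 12.8.3 uses the in-clinic score in the daily series where both scores exist for a visit date.

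**The concern.** One section treats one scale in two ways. By visit, the comparison between arms is adjusted for baseline itch and for baseline PGA, which is also the stratification factor (SAP 6: "Randomization will be stratified by baseline PGA score"). By day, no adjustment is named. SAP 12.8.2 does specify least-squares mean differences with a CI for its continuous endpoints, so their absence from the daily paragraph suggests a plain difference of mean changes. The SAP revision history places this analysis in Amendment 2, and SAP 13 gives no reason for a different method.

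The daily plot is where a reader would look for the onset of itch relief. A raw change score subtracts the whole baseline value whatever its relation to the later score. That costs precision, and any chance baseline difference between the arms feeds into every day, since all days share one baseline. At stake is the width of the daily intervals, and small unexplained differences from the ANCOVA results at visit time points.

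**Working it through.** The documents state no SD, correlation, interval width or power for the daily itch analysis, so there is no planned figure to reproduce.

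**Inputs from the documents:** about 333 and 167 subjects (SAP 6 and 7); PGA 2, 3 and 4 at about 10%, 80% and 10% (SAP 6); up to 25% lost by Week 12 (SAP 7); missing functional outcomes not imputed (SAP 9).

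**Assumptions not in the documents:** correlation r between baseline and the day's score, 0.3 to 0.9; ratio L of follow-up SD to baseline SD, 0.8 to 1.2; an NRS SD of 2.5, used only to express widths in scale points.

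**Step 1, the two variances.** Let s0 and s1 be the baseline and follow-up SDs, and K = 1/n1 + 1/n2.

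- Unadjusted difference in mean change: K × (s0² + s1² − 2·r·s0·s1)
- ANCOVA on baseline, large samples: K × s1² × (1 − r²)
- First minus second: K × (s0 − r·s1)²

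The third line is a square, so the unadjusted interval is never narrower. The two are equal only when r·s1/s0, the slope on baseline, is 1.

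**Step 2, relative width.** With s0 = s1, the unadjusted width divided by the ANCOVA width is √(2/(1 + r)). In general it is √[(1 + L² − 2rL) / (L²(1 − r²))].

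| r | L = 0.8 | L = 1.0 | L = 1.2 |
|---|---|---|---|
| 0.3 | 1.411 | 1.240 | 1.146 |
| 0.5 | 1.323 | 1.155 | 1.072 |
| 0.7 | 1.262 | 1.085 | 1.017 |
| 0.8 | 1.250 | 1.054 | 1.002 |
| 0.9 | 1.282 | 1.026 | 1.012 |

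With equal SDs the excess is 24%, 15%, 8.5%, 5% and 2.6%. Over the whole grid it runs from about 0% to 41%.

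**Step 3, check by simulation.** With 333 and 167 subjects, a 10/80/10 PGA mix, near-equal SDs and ANCOVA on baseline score and PGA, the ratios were 1.24, 1.15 and 1.08 at r = 0.3, 0.5 and 0.7, in line with the formula. PGA acted on itch only through baseline itch there, so the gain shown comes from the baseline score, and the simulation does not show what PGA would add by itself.

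**Step 4, scale points at SD 2.5, r = 0.5, equal SDs.**

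- 333 vs 167: √K = √(1/333 + 1/167) = 0.0948. The SD of change is 2.5 × √(2 × 0.5) = 2.5 and the ANCOVA residual SD is 2.5 × √0.75 = 2.165. Half-widths are 1.96 × 2.5 × 0.0948 = 0.465 unadjusted and 1.96 × 2.165 × 0.0948 = 0.402 adjusted.
- After 25% loss, 250 vs 125: 0.537 and 0.465.

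**Step 5, gap between the two estimates on one day.** The gap is (1 − slope) × the chance baseline difference. That difference has a standard error of 2.5 × 0.0948 = 0.237, so at slope 0.5 a typical gap is about 0.12 points on the 0 to 10 scale.

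**The case against.** The case for leaving the text alone is that this is a descriptive display. The SAP calls it descriptive, attaches no test to it, and leaves it out of the endpoint table in SAP 12.8 and the fixed sequence in SAP 11.6. Adjusted itch estimates already exist from Week 2, so only the detail between those time points rests on the raw difference. The gain depends on an unknown correlation, and it is probably smallest in the first days, when a score is likely to lie closest to its baseline; those are the days that matter for onset. About 84 daily models (12 weeks × 7) would be fitted to unimputed data, with roughly 17 vehicle subjects (10% of 167) in each of the mild and severe strata before dropout. The adjusted difference would also no longer equal the difference of the daily arm means beside it.

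Most of this stands, and it limits the size of the point. It does not remove it, because a between-arm difference with a 95% CI is still reported for each day, and the better model is in the same section. The small strata are not a strong obstacle: PGA entered as a three-level main effect costs two parameters. The mismatch with the raw means is real and needs a footnote.

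A reader might infer more than the documents support:

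- **That the daily estimates are biased.** Leaving missing data aside, randomization makes the raw difference unbiased. A chance baseline imbalance adds noise.
- **That the clinic-day results contradict each other.** Both methods estimate the same quantity, and the expected gap is a fraction of a point. Visits may also fall up to 2 days either side of the target at Weeks 2 to 12, so by-visit and by-day results need not match exactly under any model.
- **That the trial is short of subjects.** The width ratios can be restated as sample size, but no sample size was set for this plot.

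**Conclusion.** The point holds as a modest matter of precision and consistency. On its plain reading, SAP 12.8.3 plans an unadjusted daily difference where the same section specifies a baseline-adjusted model for the same scale. The SAP never uses the word unadjusted, so this is an inference; if ANCOVA was intended, the text still needs to say so.

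That the unadjusted interval cannot be narrower is a large-sample result and needs no assumed correlation. The amount does: about 24% wider at r = 0.3, falling to about 3% at r = 0.9 with equal SDs, and about 0% to 41% across the SD ratios considered. The documents cannot narrow this range.

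It would be wrong to conclude that any efficacy finding is at risk. The display is exploratory, the by-visit itch analyses are already adjusted, and no primary or secondary conclusion changes.

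**What to change.** In the last paragraph of SAP 12.8.3, state that for each day the treatment difference tabulated and plotted is the least-squares mean difference with its 95% CI, from the ANCOVA already given in that section (treatment, baseline PGA, baseline NRS). Keep the raw daily means by arm as descriptive statistics. Add a footnote that the adjusted difference will not exactly equal the difference of those raw means.

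The cost is one SAP sentence, one footnote and one model per day. The model is already specified, though nothing in the documents shows that it has been programmed for daily data. No extra data are needed. If the sponsor prefers the raw difference, one sentence saying that the plot is deliberately unadjusted would settle the ambiguity but forgo the precision.
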